6 STUDY OBJECTIVES

[figure not shown]
6.1 Primary Objective(s)

Table 6–1 Primary Objective(s)

Objective(s)	Endpoint(s)
To demonstrate noninferiority in visual	Binocular high contrast/high illumination
acuity at distance when wearing	(HC/HI) visual acuity (VA; logMAR) at
MF contact lenses compared to AOHG MF	distance (4 m or 3 m) at Day 30
contact lenses, after 30 days of wear.	

6.2 Secondary Objective(s)

Not applicable.

6.4 Safety Objective(s)

Table 6–3 Safety Objective(s)

Objective(s)	Endpoint(s)
To describe the safety profile of the investigational products.	Adverse eventsBiomicroscopy findings
	 Device deficiencies

7 INVESTIGATIONAL PLAN

7.1 Study Design

[figure not shown]
This is a prospective, randomized, bilateral, crossover, double-masked, trial comparing the MF and AOHG MF contact lenses.

Subjects will be randomized in 1 of 2 crossover sequences and exposed to both test and comparator lenses for bilateral wear. Subjects will be expected to attend 4 office visits and will be dispensed study lenses (test and comparator lenses) for a 30 day duration of bilateral wear with each study lens (~60 days total of study lens wear). Subjects will be expected to wear their study contact lenses for at least 8 hours per day, at least 5 days per week, over a 30 day period per study lens.

In this trial, both the investigator and subject will be masked and an unmasked site coordinator will prepare the lenses for both lens fitting and dispensing.

All study contact lenses will be prescribed according to the subject's prescription. CLEAR CARE Cleaning & Disinfecting Solution will be provided for use during the duration of the study.

Figure 7-1 Study Design

7.2 Rationale for Study Design

This study design is justified based upon an evaluation of the results of relevant preclinical and clinical testing, as described within the IB.

The bilateral, crossover study design will ensure that the same subject is exposed to both the test and comparator lens materials during the study visits and wearing period; therefore, objective and subjective assessments can be obtained for both lenses from the same subject.

The study will include only those subjects who are successful wearers of soft multifocal contact lenses in both eyes during the past 3 months for a minimum of 5 days per week and 8 hours per day. This will avoid confounding safety responses in non-adapted subjects. Habitual AOHG MF contact lens wearers are allowed to participate in this trial and can constitute up to approximately 50% of the total subject population. Habitual daily disposable multifocal soft contact lens wearers will be allowed to participate as well, and can constitute up to approximately 20% of the total subject population. The study will exclude subjects who are monovision contact lens and wearers of contact lens in one eye only.

Lubrication/rewetting drops will not be permitted during study lens wear or at study visits, as this may confound the primary effectiveness. However, habitual lubrication/rewetting drop usage is allowed up to 10 minutes prior to lens insertion and any time after lens removal during the study.

Currently pregnant or lactating women and participants with any history of amblyopia, strabismus or binocular vision abnormalities will be excluded from the trial, to prevent confounding the safety/effectiveness endpoints. Subjects who become pregnant during the study will not be discontinued; however, data will be excluded from the effectiveness analyses because pregnancy can alter refraction and visual acuity results.

7.3 Rationale for Duration of Treatment/Follow-Up

The primary will be assessed on Day 30. Hence, subjects will wear each study product bilaterally for approximately 30 days.

7.4 Rationale for Choice of Comparator Product

The AOHG MF contact lenses have been chosen as the comparator product because these lenses utilize the same Precision Profile MF design, and have the same wear modality and monthly replacement schedule as MF contact lenses.

8 STUDY POPULATION

The study population consists of volunteer subjects, of at least 40 years of age who are habitual biweekly or monthly soft multifocal contact lens wearers have at least 3 months of contact lens wearing experience, and who wear their habitual lenses at least 5 days per week and at least 8 hours per day. It is aimed to enroll (consent) approximately 96 subjects at

approximately 8 sites in the United States, with a target of 84 total subjects completed. Site-specific targets may vary based upon individual site capabilities. Estimated time needed to recruit subjects for the study is approximately 4 weeks; however, unanticipated circumstances may shorten or lengthen this time and would not require amendment of this protocol.

Habitual AOHG MF contact lens wearers are allowed to participate in this trial and can constitute up to approximately 50% of the total subject population. If enrollment exceeds approximately 50% of the target for AOHG MF habitual contact lens wearers, a subject may be discontinued at sponsor discretion. Habitual daily disposable multifocal soft contact lens wearers will also be allowed to participate and can constitute up to approximately 20% of the total subject population.

This protocol allows enrollment of the following vulnerable population(s), with associated justification for each population:

Elderly – Presbyopia and associated gradual loss of accommodation is part of the aging process and worsens with increasing age. Multifocal contact lenses are a commonly used correction option for this condition. The contact lens under study is intended to alleviate this condition. Therefore, it is appropriate and necessary to include elderly subjects in this clinical trial to gain data regarding the safety and effectiveness of the MF contact lenses in this population.

8.1 Inclusion Criteria

Written informed consent must be obtained before any study specific assessment is performed. Upon signing informed consent, the subject is considered enrolled in the study.

Subjects eligible for inclusion in this study must fulfill **all** of the following criteria:

- 1. Subject must be able to understand and sign an IRB/IEC approved Informed Consent form.
- 2. Willing and able to attend all scheduled study visits as required per protocol.
- 3. Subject must be at least 40 years of age.
- 4. Subject must be willing to stop wearing their habitual contact lenses and be willing to not wear glasses during study lens wear for the duration of study participation.

- 5. Current wearer of daily disposable and biweekly/monthly replacement multifocal soft contact lenses (including AOHG MF) in both eyes for a minimum of 5 days per week and 8 hours per day during the past 3 months.
- 6. Manifest cylinder ≤ 0.75 D in each eye.
- 7. BCVA distance (as determined by manifest refraction at screening) 20/25 or better in each eye with a spherical refractive error between -1.00 and 4.00 D, and requiring a near ADD of LO, MED or HI (ADD of +0.75 D to +2.50 D) in each eye.

Note: Study lens parameters available in this study are:

- LO ADD with -1.25 D to -4.00 D (in 0.25 D steps)
- MED ADD with -1.00 D to -4.00D (in 0.25 D steps)
- HI ADD with -1.50 D to -3.00 D (in 0.25 D steps)
- 8. Subject willing to wear the study contact lenses as defined for the full duration of the study.
- 9. Subject must possess spectacles and be willing to wear habitual spectacles for vision correction when study lenses are not worn, during wash out period and as directed by PI.

8.2 Exclusion Criteria

Subjects fulfilling any of the following criteria are not eligible for participation in this study.

- 1. Any anterior segment infection, inflammation, or abnormality or disease (including systemic) that contraindicates contact lens wear, as determined by the Investigator.
- 2. Any use of systemic or ocular medications for which contact lens wear could be contraindicated, as determined by the Investigator.
- 3. History of refractive surgery or planning to have refractive surgery during the study, or irregular cornea in either eye.
- 4. Ocular or intraocular surgery (excluding placement of punctal plugs) within the previous 12 months or planned during the study.
- 5. Biomicroscopy findings at screening that are moderate (Grade 3) or higher and/or corneal vascularization that is mild (Grade 2) or higher, and/or any infiltrate.

- 6. Current or history of pathologically dry eye in either eye that, in the opinion of the Investigator, would preclude contact lens wear.
- 7. Current or history of herpetic keratitis in either eye.
- 8. Eye injury in either eye within 12 weeks immediately prior to enrollment for this trial.
- 9. Current or history of intolerance, hypersensitivity, or allergy to any component of the study products.
- 10. Currently pregnant or lactating, as stated by subject.
- 11. Any history of amblyopia, strabismus or binocular vision abnormalities.
- 12. Any use of topical ocular medications and artificial tear or rewetting drops that would require instillation during contact lens wear.
- 13. The Investigator, his/her staff, family members of the Investigator, family members of the Investigator's staff, or individuals living in the households of the aforementioned persons may not participate in the study.
- 14. Participation of the subject in a clinical trial within the previous 30 days or currently enrolled in any clinical trial.
- 15. Monovision contact lens wearers and wearers of contact lens in one eye only.
- 16. Wearing habitual contact lenses in an extended wear modality (routinely sleeping in lenses for at least 1 night per week) over the last 3 months prior to enrollment.

8.3 Rescreening of Subjects

Rescreening of subjects is not allowed in this study.

9 TREATMENTS ADMINISTERED

9.1 Investigational Product(s)

Test Product(s): MF (LID210464)

Comparator Product(s) (If applicable):

AOHG MF

Table 9–1 Test Product

Test Product	Multifocal contact lenses (MF)						
	LID210464						
Manufacturer	Alcon Laboratories, Inc.						
	[name]						
	[name]						
	USA						
Indication for use and intended purpose in the current study	The investigational frequent replacement multifocal contact lens is indicated for the optical correction of presbyopia with or without refractive ametropia (myopia and hyperopia) in phakic or aphakic persons with non-diseased eyes who may require a reading addition of +3.00 diopters (D) or less and who may have up to approximately 1.50 diopters (D) of astigmatism that does not interfere with visual acuity.						
Product description	Material: lehfilcon A						
and parameters	• Water content: 55% (targeted)						
available for this	Power range:						
study	o LO ADD with -1.25 D to -4.00 D (in 0.25 D steps)						
	spherical power as available						
	o MED ADD with -1.00 D to -4.00D (in 0.25 D steps) spherical power as available						
	o HI ADD with -1.50 D to -3.00 D (in 0.25 D steps)						
	spherical power as available						
	Base curve (mm): 8.4 mm (targeted)						
	Diameter (mm): 14.2 mm (targeted)						
Formulation	Refer to IB						
Usage	• Wear:						
	o Daily Wear						
	o Bilateral						
	Replacement period: 30-day replacement						
	• Exposure: At least 8 hours per day, 5 days per week, over a 4-						
	week period.						

	 Lens Care: Cleaned and disinfected with CLEAR CARE Cleaning & Disinfecting Solution after each use Replacement lenses will not be provided to the subject. In the event a lens needs to be replaced, the subject must return to the site for a replacement lens. Until the replacement lens is obtained, the subject must store both study lenses in the provided lens care solution and wear their habitual spectacles. 	
Number/Amount of	Subjects will insert study lenses at Visit 2 and Visit 3 at the site.	
product to be	No spare lenses will be provided to the subject.	
provided to the		
subject		
Packaging	Blister foil pack	
description		
Labeling description	Lens Foil label includes at a minimum:	
8 1	- material name and identifier	
	- base curve	
	- diameter	
	- manufacturing protocol number	
	- packing solution	
	- power	
	- lot number	
	- expiration date	
	- content statement	
	- investigational device statement	
	- sponsor information	
	• Provided in ~15 lenses per power per package, identified with	
	the following at a minimum:	
	- a color coded label stating the protocol number	
	- LID number	
	- power	
	- an investigational use only statement- Handling unit	
Training and/or	No additional training or experience is required to administer the	
experience	test product.	
- CAPOTTOTION	toot product.	

requirements for		
device		
Storage conditions	Lenses are to be stored at room temperature	
Supply	 Lenses supplied by the sponsor CLEAR CARE Cleaning & Disinfecting Solution supplied by sponsor to be provided to the subject LacriPure saline will be permitted for rinsing the lens(es) after removal and prior to insertion, if required. 	

Table 9–2 Comparator Product

Comparator	AIR OPTIX plus HydraGlyde Multifocal contact lenses (AOHG			
Product(s)	MF)			
Manufacturer	Alcon Laboratories, Inc.			
	[name]			
	[name]			
	USA			
Indication for Use	These comparator multifocal soft contact lenses are indicated for the optical correction of presbyopia, with or without refractive ametropia (myopia and hyperopia) in phakic or aphakic persons with non-diseased eyes who may require a reading addition of +3.00 diopters (D) or less and who may have up to approximately 1.50 diopters (D) of astigmatism that does not interfere with visual acuity.			
Product description	Material: lotrafilcon B			
and parameters	• Water content: 33%			
available for this				
study	• Power range: Limited lens parameters will be available for use in this study:			
	 LO ADD with -1.25 D to -4.00 D (in 0.25 D steps) spherical power as available MED ADD with -1.00 D to -4.00 D (in 0.25 D steps) spherical power as available HI ADD with -1.50 D to -3.00 D (in 0.25 D steps) spherical power as available 			
	Base curve (mm): 8.6 mm			

	Diameter (mm):14.2 mm	
Formulation	Refer to package insert	
Usage	 Wear: Daily Wear Bilateral Replacement period: 30-day replacement Exposure: At least 8 hours per day, 5 days per week, over a 4-week period. Lens Care: Cleaned and disinfected with CLEAR CARE Cleaning & Disinfecting Solution after each use Replacement lenses will not be provided to the subject. In the event a lens needs to be replaced, the subject must return to the site for a replacement lens. Until the replacement lens is obtained, the subject must store both study lenses in the provided lens care solution and wear their habitual spectacles. 	
Number/Amount of Product to be Provided to the subject	 Each site will procure their own comparator lenses. Subjects will insert study lenses at Visit 2 and Visit 3 at the site. No spare lenses will be provided to the subject. 	
Packaging description	Commercial packaging	
Labeling description	Commercial foil	
Training and/or experience requirements for device	No additional training or experience is required to administer the comparator product.	
Storage conditions	Lenses are to be stored at room temperature	
Supply	 Each site will procure their own comparator lenses. CLEAR CARE Cleaning & Disinfecting Solution supplied by sponsor to be provided to the subject LacriPure saline will be permitted for rinsing the lens(es) after removal and prior to insertion, if required. 	

9.2 Other Medical Device or Medication Specified for Use During the Study

No other medical devices or medications are required to be used in conjunction with the treatments during the clinical study.

9.3 Treatment Assignment / Randomization

Subjects will be randomized in a 1:1 ratio to receive treatment in crossover sequence test product then comparator product or comparator product then test product, respectively.

Sequence	EDC/randomization integration system	Lens Name
Sequence 1	LID210464/AOHG MF	MF/AOHG MF
Sequence 2	AOHG MF/LID210464	AOHG MF/

[figure not shown]
Only after signing the ICF, a subject will be assigned a subject number by the electronic data capture system.

[figure not shown]
A randomization list will be generated using a validated system that automates the random assignment of treatment arms to randomization numbers in the specified ratio. Subjects will be assigned treatment according to the randomization list uploaded in the randomization system. The randomization list will be generated and maintained by the study sponsor.

At Visit 1, all eligible subjects will be randomized via the EDC/randomization integration system to one of the treatments (lens sequences). The investigator's delegate will access the respective system after confirming that the subject meets all the eligibility criteria. A randomization number will be automatically assigned to the subject according to the subject randomization list but will not be communicated to the site user. The EDC/randomization integration system will inform the site user of the treatment (lens sequence) assignment to be dispensed to the subject. The same randomization assignment will be followed for lens fitting.

9.4 Treatment Masking

This study is double-masked, with subjects randomized to use MF or AOHG MF contact lenses for the duration of the 30 day treatment period.

This level of masking will be maintained throughout the conduct of the study. Unmasking will occur only after all planned study data have been validated, and the database locked.

Masked study personnel must avoid seeking information that may compromise masking.

In the event of a medical emergency where the knowledge of subject treatment is required, an individual investigator will have the ability to unmask the treatment assignment for a specific subject after contacting an appropriate study sponsor representative if time allows.

9.5 Accountability Procedures

Upon receipt of the IPs, the investigator or delegate must conduct an inventory.

This record must be made available to the study monitor for the purposes of verifying the accounting of IP supplies. Any discrepancies and/or deficiencies between the observed disposition and the written account must be recorded along with an explanation. All IPs sent to the investigator must be accounted for by study sponsor personnel, and in no case be used in an unauthorized situation.

The investigator should make every effort to collect unused lenses, foils, and supplies from subjects.

It is the investigator's responsibility to ensure that:

- All study products are accounted for and not used in any unauthorized manner
- All unused products are available for return to the study sponsor, as directed
- Any study lenses associated with a device deficiency or with any product-related adverse event (i.e., ADE or SADE) are returned to the study sponsor for investigation, unless otherwise directed by the sponsor. Refer to Section 11 of this protocol for additional information on the reporting of device deficiencies and AEs and the return of study products associated with these events.

The investigator is responsible for proper disposition of all unused IPs at the conclusion of the study, according to the instructions provided in the MOP.

9.6 Changes to Concomitant Medications, Treatments/Procedures

After the subject is enrolled into the study, the investigator must instruct the subject to notify the study site about:

- Any new medications
- Alterations in dose or dose schedules for current medications
- Any medical procedure or hospitalization that occurred or is planned
- Any nondrug therapies (including physical therapy and blood transfusions)

The investigator must document this information in the subject's case history source documents.

10 STUDY PROCEDURES AND ASSESSMENTS

10.1 Informed Consent and Screening

The investigator or delegate must explain the purpose and nature of the study, and have the subject read, sign, and date the IRB/IEC-approved informed consent document. The subject must sign the ICF BEFORE any study-specific procedures or assessments can be performed, including study-specific screening procedures. Additionally, have the individual obtaining consent from the subject and a witness, if applicable, sign and date the informed consent document.

The investigator or delegate must provide a copy of the signed document to the subject and place the original signed document in the subject's chart, or provide documentation as required by local regulations.

10.2 Description of Study Procedures and Assessments

Study-specific procedures and assessments described here may include standard of care; other standard of care procedures performed in the clinical management of the subject are not excluded.

Detailed descriptions of assessments and procedures are provided in the MOP. The investigator is responsible for ensuring responsibilities for all procedures and assessments are delegated to appropriately qualified site personnel.

10.2.1 Demographics

Obtain demographic information including age, race, ethnicity, and sex.

10.2.2 Medical History and Concomitant Medication

Collect medical history information for the past year, including information on all medications used within the past 30 days. Include herbal therapies, vitamins, and all over-the-counter as well as prescription medications. Throughout the subject's participation, obtain information on any changes in medical health and/or the use of concomitant medications.

Targeted Medical History and Concomitant Medications will be collected in the eCRF as outlined in the MOP.

10.2.3 Lens Fitting

During Visit 1, the investigator should determine if a subject meets the qualification of Inclusion Criteria #7 based upon their habitual contact lens prescription and screening manifest refraction, indicating that a subject could be fit within the available study lens parameters. In this trial, lens fitting assessments are performed after screening and confirmation of Inclusion/Exclusion criteria, and after a subject is randomized. If a subject meets Inclusion Criteria #7 during screening, but at the time of lens fitting, is determined by the PI to be unable to wear study lenses in the available parameters (for both test and comparator), the subject should be discontinued from the study as an Early Exit, and not categorized as a screen failure.

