(See Section 8.1 for a	aged \geq 40 years with normal eyes (other than correction for						
complete list of	refractive error). Subjects should have at least 3 months						
-	wearing experience, wear these lenses at least 5 days per week						
inclusion criteria)	and at least 8 hours per day.						
	• Subjects must have a manifest cylinder ≤ 0.75 D in each eye.						
	• Subjects must have a BCVA of 20/25 or better in each eye at						
	distance with a spherical refractive error between -1.00 and -4.00 D, and requiring a near ADD of LO, MED or HI (ADD						
	of $+0.75$ D to $+2.50$ D) in each eye.						

Key exclusion Currently pregnant or lactating criteria Any history of amblyopia, strabismus or binocular vision abnormalities (See Section 8.2 for a Monovision contact lens wearers and wearers of contact lens in complete list of one eye only. exclusion criteria) Data analysis and **Planned Data Analysis** sample size justification planned analyses are summarized below: **Endpoint** Statistical Model Comparison Primary Mixed effects repeated Binocular MF vs HC/HI VA at AOHG MF measures Sample Size Justification Sample size calculation is based on 2 prior clinical studies which evaluated performance of several marketed multifocal contact lenses. Of the endpoints with planned inferential testing, VA at near yields the largest required sample size of 42/sequence at 90% power, one-sided α =0.05, with NI margin of 0.05. Associated materials CLEAR CARE® Cleaning & Disinfecting Solution Lubrication/rewetting drops will not be permitted during lens wear. However, habitual lubrication/rewetting drop usage is allowed up to 10 minutes prior to lens insertion and any time after lens removal. • No lubrication/rewetting drop use will be allowed during clinic

removal and prior to insertion, if required.

LacriPure saline will be permitted for rinsing the lens(es) after

Table 3-1 Schedule of Study Procedures and Assessments

			IS 1 od 1)	LENS 2 (Period 2)			
	Visit 1 Screening / Baseline / Lens Fit	Visit 2 Dispense Lens 1	Visit 3 Day 30 Follow-up Lens 1	Visit 3 Dispense Lens 2	Visit 4 Day 30 Follow-up Lens 2 / Exit	Unscheduled Visit	Early Exit
Procedure/ Assessment		Day 1 [3-5 days after Visit 1	Day 30 (- 2/+1) Days	Day 1 [same day as Lens 1 Day 30 Follow-up visit]	Day 30 (- 2/+1) Days	N/A	N/A
Informed Consent	X						
Demographics	X						
Medical History [∞]	X	X	X		X	X	X
Concomitant Medications [∞]	X	X	X		X	X	X

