10.4 Discontinued Subjects

10.4.1 Screen Failures

Subjects who were excluded from the study after signing the informed consent and prior to randomization to product/dispense of study product.

The investigator must document the reason for screen failure in the subject's case history source documents.

Subject numbers must not be re-used.

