10.4.2 Discontinuations

Discontinued subjects are individuals who voluntarily withdraw or are withdrawn from the study by the investigator after signing informed consent and after randomization.

Subject numbers of discontinued subjects must not be re-used (i.e., subject replacement is not allowed).

Subjects may discontinue from study or study treatment at any time for any reason. Subjects may also be discontinued from study treatment at any time if, in the opinion of the investigator, continued treatment poses a risk to their health.

If a subject discontinues from study treatment, every effort must be made to keep the subject in the study and to continue with the study assessments as specified in the schedule of study procedures and assessments until the final visit.

For subjects discontinuing from the study, the investigator must complete all Exit procedures according to Table 3–1 Schedule of Study Procedures and Assessments and Section 10.4.3, if the subject is willing and able, and if in the opinion of the investigator it is safe for the subject to do so.

The investigator must document the reason for study or treatment discontinuation in the subject's case history source documents.

To ensure the safety of all subjects who discontinue early, investigators must assess each subject and, if necessary, advise them of any therapies and/or medical procedures that may be needed to maintain their health.

10.4.3 Schedule of Procedures and Assessments for Subjects Discontinued from Investigational Product

Other than screen failures, if a subject discontinues from the study, the subject should undergo an Early Exit Visit, as possible. Refer to Table 3–1.

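### Do criterion 7, the lens-fitting rule and the screen-failure definition leave it unclear who is eligible and how a fitting failure is handled?

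*Protocol*

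**What the plan says.** **Eligibility.** The Protocol Summary (Section 3) states criterion 7 with one range for every ADD: "spherical refractive error between -1.00 and -4.00 D, and requiring a near ADD of LO, MED or HI". The Note under criterion 7 in Section 8.1, and Tables 9-1 and 9-2, list narrower lens ranges for two of the three ADDs. LO starts at -1.25 D, and the high-ADD entry is "HI ADD with -1.50 D to -3.00 D (in 0.25 D steps"). MED covers the whole range.

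**Fitting.** Section 10.2.3 has the investigator judge criterion 7 from the habitual lens prescription and the screening refraction, "indicating that a subject could be fit within the available study lens parameters". Fitting follows randomization. A subject who met criterion 7 but then "is determined by the PI to be unable to wear study lenses in the available parameters (for both test and comparator") leaves as an Early Exit, and the section expressly says this is not a screen failure. Table 3-1 places fitting of both lenses at Visit 1 and the first dispensing at Visit 2, 3 to 5 days later.

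**Classification.** Section 10.4.1 defines screen failures as exclusions "prior to randomization to product/dispense of study product". Section 10.4.2 covers subjects who withdraw or are "withdrawn from the study by the investigator after signing informed consent and after randomization".

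**Analysis set.** Protocol 12.2.2 admits randomized subjects exposed to any study lens, not counting the lenses used for fitting at Visit 1.

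**The concern.** Two sites could treat the same subject differently in three ways.

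1. A site reading criterion 7 literally could randomize someone for whom no listed lens exists. A site following 10.2.3 would screen that person out.
2. The parenthesis in 10.2.3 could mean that neither lens can be worn, or that both must be wearable. The sphere and ADD ranges are the same for the two lenses, but material and base curve differ: Table 9-1 gives "Base curve (mm): 8.4 mm (targeted") for the test lens and Table 9-2 gives 8.6 mm for the comparator. Failure on one lens only is therefore conceivable. If such a subject went on, the full analysis set would contain a subject with data on one lens, although Section 7.2 says the design "will ensure that the same subject is exposed to both the test and comparator lens materials".
3. If the screen-failure window runs to dispensing, a fitting failure is a screen failure under 10.4.1 and a discontinuation under 10.2.3 and 10.4.2. The label affects the disposition table and whether an Early Exit Visit applies under 10.4.3.

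At stake would be consistent handling of subjects lost after randomization and, at worst, the make-up of the primary analysis set.

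**Working it through.** **Step 1: size of the eligibility gap.** The inputs are the criterion 7 range and the lens ranges in its Note. The text of 8.1 shows the upper limit without its minus sign; the Protocol Summary gives -4.00 D, which is used here.

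| ADD | Sphere steps under criterion 7 | Listed lenses | Not covered |
|---|---|---|---|
| LO | 13 | 12 | -1.00 |
| MED | 13 | 13 | none |
| HI | 13 | 7 | -1.00, -1.25, -3.25, -3.50, -3.75, -4.00 |
| Total | 39 | 32 | 7 |

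Steps of 0.25 D from -1.00 to -4.00 D give 3.00/0.25 + 1 = 13 powers, so 13 × 3 = 39 combinations, and 39 - 32 = 7. This counts combinations per eye, not subjects. It also treats refractive sphere as lens power. Criterion 7 is about the first and the Note about the second, so vertex or over-refraction adjustment could move the count by a step.

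**Step 2: does the text already deal with those combinations?** Section 10.2.3 makes the lens list the test of criterion 7, and the Note is printed inside the criterion. Followed as written, uncovered combinations stop at screening. Anyone who passes screening and still cannot be fitted has a stated outcome in the same section.

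**Step 3: the one-lens case.** Four places bear on how to read the parenthesis:

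- Table 3-1 requires fitting of both test and comparator at Visit 1.
- Section 7.1 has every subject wear both lenses.
- Section 9.3 randomizes only to two-lens sequences.
- Criterion 8 requires willingness to wear the study lenses for the full study.

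No visible passage provides for dispensing one lens and skipping the other, or for starting in Period 2. The reading that fits the design is that both lenses must be wearable.

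**Step 4: the screen-failure cut-off.** If the slash in 10.4.1 is read as randomization, 10.2.3, 10.4.1 and 10.4.2 all agree. If it is read as dispensing, a loosely punctuated general definition contradicts a specific rule written for exactly this case. The specific rule governs.

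**Step 5: effect on the primary analysis.** SAP Section 7 gives an SD of the paired difference of 0.0845, a margin of 0.05, one-sided α = 0.05, 90% power and 13 per sequence.

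- Reproducing the SAP figure: N = [0.0845 × (1.645 + 1.282) / 0.05]² = 24.46, so 25 in total and 13 per sequence (26) after rounding. The figure reproduces.
- Power at other sizes uses the noncentral t with N - 2 degrees of freedom, noncentrality 0.05√N/0.0845 and a true difference of 0.

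| Completers | Power, distance VA |
|---|---|
| 26 | 90.1% |
| 72 | 99.96% |
| 80 | 99.98% |
| 84 | 99.99% |

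Enrolling about 96 for 84 completers leaves 12 (12/96 = 12.5%) for every kind of loss. A subject who can wear only one lens supplies no within-subject lens difference on either reading, so the number of complete pairs does not depend on how the parenthesis is read.

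**The case for a change.** The strongest case for acting is uniformity. With about eight sites and no replacement of subjects, exits after randomization should be classified in one way, and a definition should not turn on how a slash is read. The edits would be cheap and would leave sample size, randomization, masking and model alone. There is also less slack elsewhere: the Protocol Summary says near VA drives the size, at 42 per sequence. Back-calculating, the implied SD is 0.05 × √84 / 2.926 = 0.157, and on the normal approximation power for that endpoint would fall from 90% at 84 completers to 88.7% at 80 and 85.6% at 72.

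Part of this stands. Criterion 7 does not expressly call its Note binding, 10.2.3 does not set out the one-lens case separately, and the slash is loose drafting.

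The rest does not carry the point. On the one-lens case, criterion 7, its Note and 10.4.1 are silent, and silence is not disagreement. The near-VA figures describe losing completers for any reason; rewording these sections would not make an unfittable subject fittable. Whether a subject is in the full analysis set is already settled by the exposure rule in Protocol 12.2.2. SAP Section 3 already plans disposition by sequence and a listing of discontinued subjects, so a separate exit reason is a preference.

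**Conclusion.** No change to the plan is needed. Each point is a drafting gap that the surrounding text fills sensibly: 10.2.3 links eligibility to the lens list and names the category for a fitting failure, 10.4.2 agrees with it, and the crossover design points to requiring both lenses. Handled that way, a subject who cannot be fitted leaves before dispensing and falls outside the full analysis set.

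The measurable gap is about 7 of 39 sphere/ADD combinations, give or take a step. Power for the primary endpoint stays above 99.9% from 72 to 84 completers, and no bias in the lens comparison is shown. The most that could differ between sites is a disposition label, or the occasional subject with data on one lens only.

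This rests on three assumptions: the SAP's SD of 0.0845 with a true difference of zero; sites following the specific rule in 10.2.3 over the general definition in 10.4.1; and fitting failures being few. The documents give no rate for such failures, and none is estimated here. The Manual of Procedures, which holds the detailed fitting instructions, was not available. If the protocol is amended for another reason, the three wordings could be aligned then.
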